Analyses will determine if change in potential mediators from baseline to 12 months predict weight loss at 24 months. Analyses will determine whether temporally precedent changes in hypothesized mediators explain the effect of condition on weight loss, with the expectation that the Share ON participants will maintain a high level of the proposed mediator from baseline to 12 months, while decreases in that variable will be observed in Share OFF. Coach Share, Group Share, and Friend/Family Share will each be examined separately, with possible mediators including perceived supportive accountability, motivation, self-regulation, and self-monitoring. In addition, coaching quality will be examined as a mediator for Coach Share ON vs. OFF, social comparison will be examined as a mediator for Group Share ON vs. OFF, and perceived social support will be examined as a mediator for Friend/Family Share ON vs. OFF. We will use the mediation model outlined by Preacher and Hayes to estimate the indirect effect of each hypothesized mediator individually. The bias-corrected bootstrap test will be applied to test the significance of the indirect effect, which allows for the most robust and accurate interpretation of the mediating effects. Should these mediation analyses prove promising, we will explore how the entire pattern of changes in the mediators from baseline to later time periods influences the corresponding pattern of weight loss over time using parallel process growth models.

Aim 3

To test if intervention effects depend on quality of the relationship with the coach, group members, or friend/family member, relationship quality will be examined as a potential moderator by adding it to the multilevel model described in Aim 1 and determining whether the effect of condition on change in weight depends on this variable. Relationship quality will be examined at baseline, and also will be examined separately at 6 and 12 months (controlling for weight loss up to that point). Statistically significant interactions will be interpreted by plotting simple regression lines for high and low values of this variable. To analyze qualitative data, transcribed interviews will be coded for thematic analysis. Coding steps will include the development of preliminary themes,

additional codes based on themes that arise, non-substantive codes, and detailed codes for analysis of specific topics. We will create a coding dictionary based on analysis of the first five transcripts, and every fifth subsequent transcript will be double-coded in order to assess interrater reliability. If there is <90% agreement in coding, we will re-assess domains to identify areas in which different labeling may have been used for similar ideas.

Power analyses suggest that a sample size of 238 is required for 80% power with the significant level of 0.05 and four assessment points, assuming the ratio of the variability of level-1 coefficient to the variability of level-1 residual is at least one. The study is adequately powered with the proposed sample size of 320 with up to 25% attrition.

c) **Withdrawal of Subjects**

Participants will be withdrawn from the research without their consent if there is a change in the subject's medical condition, if all or part of the study is discontinued for any reason by the sponsor, investigator, university authorities, or government agencies, new information is available to the investigator, or there are harmful unforeseen reactions experienced by the participant or other participants in the study. Participants will be notified about any new information that may affect their health, welfare, or choice to stay in the research.

If the friend/family member identified by the index participant does not consent to participate in the study, the index participant will be asked to identify another friend/family member. If they cannot find another friend/family member who would be willing to consent to the study (which is an inclusion criteria), then the index participant will be deemed ineligible and provided with relevant weight loss referrals.

Index participants and friends/family members may withdraw from the study at any time, and it will not be held against them. If an index participant or friend/family member stops being involved in the research, already collected data may not be removed from the study database. Any fee the index participant or friend/family member may be paid will be determined by the amount of time they spend in the trial and, if they do not complete the study, the reason for leaving the study early.

If termination is necessary, the project coordinator will contact the index participant or friend/family member immediately to discuss the grounds for their termination.

2) **Risks to Subjects**

Potential risks to participants are considered minimal. Participants will be informed of all potential risks when providing consent and assent before study participation. However, key personnel will address any discomfort or concerns expressed by the participant in regard to any aspect of the study if they do occur. If participants indicate any substantial distress, then risk assessment will occur and appropriate referrals for treatment will be provided as necessary.

One risk of the program is that as index participants lose weight, they may need to take less of any medications they are on, or they may develop gallstones. Index participants taking any medication will be instructed to carefully coordinate the oversight of these

medications with their primary care physicians to make any necessary adjustments of dosage necessary if weight loss occurs. Gallstones can result if weight is lost too quickly, but our study is designed to help individuals lose weight at only approximately 1-2 pounds per week. When using exercise equipment, however briefly, there is always a risk for injury if adequate precautions are not taken. In addition, PA may be uncomfortable to those index participants who are inactive or overweight, or may cause exacerbation of certain medical conditions. However, this is unlikely given the moderate recommendation (walking). An Adverse Event Questionnaire will be administered to all participants at 6, 12, and 24 months. This questionnaire will collect information about any medical events that have occurred during the course of the program. If an adverse event is reported and more information is necessary, an interview will be conducted with the participant to collect the additional information. This information will then be reported to NIH.

Psychological risks include reduced self-esteem in persons who fail to lose weight or regain weight, a sense of shame if not meeting program goals, or fellow program members or friends/family making critical remarks about an individual's weight or LM habits. However, several precautions will be taken to guard against psychological risks to participants. A methodical process of treatment development will be carried out to ensure that participant needs are met in a sensitive, caring, and culturally competent way. All clinicians will have had prior training and experience delivering LM programs. In addition, clinicians will receive specialized training in the delivery of the intervention programs, in particular how to monitor, respond to, and prevent participant feelings of shame or embarrassment. [name] will take responsibility for ensuring that adequate training and supervision are provided, with assistance from the study co-investigators.

There also is a risk that group members or the designated friend/family member could share information about that index participant outside of the program. For both index participants and friends/family members, there is the risk that having the friend/family member serve in a support role could introduce a strain in the relationship. In all conditions in which any form of data sharing occurs, the coach will regularly discuss with participants any concerns they have about data sharing, so that problem can be addressed (e.g., if a data sharing friend/family member is making critical remarks, the index participant can be coached how to address this with that party, or that party can be replaced with a different friend/family member for data sharing). Coaches will be given training in how to assess any possible iatrogenic effects of data sharing that are disclosed by index participants (e.g., relationship strain with the data sharing partner), and coaches will log all such reports in a REDCap field to allow for trial monitoring and reporting.

Several steps will be taken to protect index participant confidentiality in the context of group-based treatment. At the first group meeting the importance of confidentiality will be discussed and concrete guidelines will be provided regarding permissible versus inappropriate disclosure of information about group-based treatment to others, including via social media (e.g., when discussing this LM program with other parties, the focus should be limited to one's own experience, not what is shared by others in group; names and identifying details of other index participants should never be disclosed to others; etc.). To maximize adherence to these guidelines, they will be presented in a way that elicits feedback from the group (so that group members have a sense of ownership

regarding these norms) and index participants will be encouraged to publicly commit in group to upholding these standards of confidentiality. Index participants will be notified that failure to respect the confidentiality of other group members is grounds for dismissal from the program. Similar training about confidentiality will be conducted with designated friends/family members who participate in the program to support an index participant's LM efforts.

3) Potential Benefits to Subjects

Participants may or may not benefit directly from this study. It is possible that the intervention may promote healthy behaviors, such as increasing physical activity and reducing caloric consumption, which may benefit index participants psychologically and medically. Also, the prescribed behavioral changes for index participants are known to promote improved quality of life and positive health outcomes. Participants in LM programs typically report that mood and quality of life also improve during the course of the program.

4) Privacy and Confidentiality

This study will not use nor disclose Protected Health Information (PHI).

As per policy of the IRB, all participant data, including the fact of their participation, will be treated as confidential and will be safeguarded according to the practices described above. All study staff will be trained regarding the importance of confidentiality, and all possible efforts to protect participant privacy will be observed. Participant materials will be labeled with a study identification number rather than personally-identifiable information (e.g., name). All data will be stored in password-protected files on secure servers that are only accessible to identified study staff. After being stripped of identifiable information, written materials from participants will be stored in locked filing cabinets. Drexel University Institutional Review Board and HIPAA guidelines will be observed.

Privacy and confidentiality will be explained to participants during the consent process, and questions about privacy will be answered as needed throughout the study. Participants will be reminded that they can decline to answer person questions as appropriate (e.g., during assessments). They also will be provided with contact information for the principal investigator and community mental health resources, to be used in the event of unforeseen distress.

[name] will administer a data collection and storage training to all project staff, who must demonstrate competence in all tasks (e.g., phone screening, informed consent, etc.) before commencing their responsibilities. Staff will be assigned to review assessment data for accuracy and completion, and to pursue missing data by re-contacting participants. Specialized validity tools (e.g., customized spreadsheets and data entry software) will be used to maximize data accuracy. Double-entry will be utilized where appropriate. To maximize efficiency, data will be electronically managed through REDCap, a secure application that has been successfully used by this team on several projects. All paper-based data will be stored in a locked filing

cabinet, and all electronic data will be password protected and stored on secure computer servers. On-site and off-site backup storage will be utilized to protect against loss.

All data given to the statistician, as well as given to the DSMP-identified security officer, will be masked and, therefore, will contain no identifying information, except as required when reporting adverse events. No identifying information will be contained within study databases. All research data will be kept separate from identifiers and linked with a participant number. Only [name] and her research coordinator will have access to the file linking names and participant numbers, and this file will be stored in their locked offices.

5) **Economic Burden to Subjects**

This research includes free assistance with developing healthy eating and physical activity and use of a commonly used digital self-monitoring device and wireless scale. Index participants will be financially compensated for their time spent in assessments.

Index participants and friend/family members are required to have access to a smartphone and data plan for using the study app. Financial assistance will be provided as needed for this technology or for text message costs.

6) **Subject Compensation**

Index participants can earn up to \$140 for participating in this study, contingent upon the completion of all assessment assignments.

Index participants will be paid \$40 for completing the 6-month assessment, \$50 for completing the 12-month assessment (mid-treatment), and \$50 for completing the 24-month (post-treatment) assessment. Compensation is contingent upon participants completing assigned study tasks.

Wave 1 participants who volunteer to complete the optional ecological momentary assessment study will receive an additional \$75, making their total compensation \$215.

The selected friend/family member involved in the study intervention will be compensated \$50 upon completion of their webinar attendance.

Payment will be provided for index participants and friend/family members as an e-gift card from Amazon or through direct ACH payments to the participant's bank account. ACH is a very common, secure and fast electronic payment method used by all major banks. The use of ACH as a payment option allows for remote payment and helps us protect the privacy and safety of the participants and the research staff. To use this form of payment, we will provide JPMorgan Chase Bank the participant's study ID, name, and email or phone number. Chase will then send the participant an invitation to receive payment either as an email or a text message. Once the participant accepts the invitation, the funds will be deposited to their bank

account. Drexel University and the research team do not have any access to the participant's account information and are not directly involved in the disbursement of the funds.

If participants cannot or do not want to receive a direct, electronic payment nor an e-gift card, they will have the option of receiving a check from Drexel University. This option takes several weeks to process, requires the participant to complete a federal W9 form and requires disclosing their name and social security number to Drexel's Accounts Payable department. They will also need to disclose their name and address to JPMorgan Chase Bank, who would be the distributor of the check.

7) Consent Process

The consent process will follow the IRB recommended “Investigator Guidance: Informed Consent (HRP-802)” document. Index participants will be told that the purpose of the study is to test new approaches to supporting long-term behavior change, specifically, that this study will test whether using coaches, program peers, or family/friends as sources of support and accountability can improve long-term weight loss. They will be told participation is voluntary and they can withdraw from the study at any time. Participants will be sent a copy of the screening consent before the phone screen. They will be prompted to ask any questions and will be assessed for comprehension. After reviewing the form and clarifying any confusion, signatures will be collected. If the participant chooses not to sign the screening consent, the phone screen will not continue.

At the end of the clinic visit, each index participant will be given a copy of the full study consent form. Participants will then review the consent form ahead of their Session 0. At Session 0, a staff member will review the consent in detail and the index participant will digitally sign and return it if.

Full eligibility will not be determined until following the study visit. Index participants will be explicitly informed that their eligibility is still not final at the conclusion of the study visit. There may be some occasions on which it is more subjective whether a prospective participant meets the inclusion or exclusion criteria (e.g., psychiatric condition) and so eligibility cannot be confirmed immediately during the study visit. Throughout the enrollment process, we will hold consensus meetings where these types of enrollment decisions and questions will be reviewed by staff and investigators. We cannot inform index participants of their final eligibility until after these meetings are held and criteria are discussed. Index participants will be contacted after the visit to confirm whether they are enrolled. We do expect that a small number of index participants will be deemed ineligible after the consensus meeting. We will make a phone call to these participants and provide relevant weight loss referrals.

Wave 1 participants who are invited to participate in the optional ecological momentary assessment will be sent an electronic version of the informed consent form to digitally sign and return. Changes to the original informed consent will be clearly highlighted.

[name] will provide several hours of training to familiarize study staff with the process of properly obtaining informed consent. Before signatures are collected, participants will be asked the following questions to assess their understanding of the risks and benefits of participation:

- What are we going to ask you to do as part of this study?
- What time commitment will the study require?
- What are the main risks and benefits of participating?

Friend/family members who have been selected by index participants will be sent an email from the research team with study details and a link to provide consent digitally and to complete self-report measures. The friend/family member will be given the opportunity to sign up for a study visit with study staff if they have additional questions. This session will give adequate time for friends/family members to understand the study and ask any questions.

8) Process to Document Consent in Writing

We will be following “INVESTIGATOR GUIDANCE: Informed Consent (HRP-802).” Fitlink Informed Screening Consent Form will be sent out to index participants prior to scheduled phone screen with Fitlink screeners. If participants do not complete the Informed Screening Consent Form before scheduled phone screen, screeners will guide participants to read the consent form. They will then be asked to sign the screening consent via a REDCap survey and encouraged to contact the PI at any time if they have any questions or concerns.

The Index Participant Informed Consent Form will be provided to participants after the clinic visit is complete. The participant will review it ahead of their Session 0. At Session 0 participants will have time to ask any questions that they may have. They will then sign the form via an online REDCap survey and submit. Participants will be encouraged to contact the PI at any time if they have any questions or concerns.

Friends/family members will be provided with a digital consent form before they begin any self-report measures. After friends/family read the consent, they will be asked if they have any questions regarding the research and a member of the research team will be available to read through the consent and answer questions. They will then be asked to sign the consent and encouraged to contact the PI at any time if they have any questions or concerns.

9) Vulnerable Populations

Does not apply.

10) Multi-Site Human Research

Does not apply.

11) Sharing of Results or Incidental Findings with Subjects

Findings will be disseminated to the research and practice communities through presentations at professional conferences and publication of results in peer-reviewed journals. We will register our clinical trial at ClinicalTrials.gov before subject recruitment and ensure that summary results data are submitted there in a timely fashion (e.g., participant flow, baseline characteristics, outcome measures, statistical analyses, data on adverse events). Our informed consent documents will include specific statements related to posting information and results at ClinicalTrials.gov.

Consent forms will also explain that all data will be de-identified prior to the registration of results in order to protect participant privacy and confidentiality. Drexel University has an internal policy in place to ensure that clinical trial registration and results reporting occur in compliance with NIH policy requirements. We will assume full responsibility for following the appropriate requirements and timelines.

12) Research Conducted in a Foreign Country

Does not apply

13) Community-Based Participatory Research

Does not apply

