Perceived supportive accountability for weight control will be measured with the Supportive Accountability Measure. Self-regulation will be measured with the Helpfulness of Program Components measure. Self-monitoring will be objectively measured as the number of days in which digital devices were used to measure weight, record eating (with a minimum threshold of 5 foods/beverages recorded), or PA (minimum threshold of 500 steps). Coaching quality will be assessed by rating 15% of each coach's group sessions, text messages, and phone calls with a rubric adapted from the ASPIRE-VA checklist. The tendency for participants to engage in social comparison with fellow LM group members will be measured with the Iowa-Netherlands Comparison Orientation Measure, with items modified to be focused on the LM group, and with the FitLink Social Comparison Measure. Perceived social support will be assessed with the Social Support for Healthy Behaviors measure. Index participants will report the frequency with which friends and family members engaged in behaviors that support or undermine healthy eating and physical activity in the past month. Quality of group and friend/family interactions will be assessed with the Quality of Interactions measure. Weight stigma will be assessed using the Weight Self-stigma Measure. A demographic questionnaire will also be administered to participants at the baseline assessment. The Power of Food Scale will be used to assess individual reactions to food in their environment. The food environment will be assessed with Grocery Shopping and Home Food Environment Items. Food Addiction will be assessed using the Modified Yale Food Addiction Scale 2.0 (mYFAS 2.0). Utilization of stimulus control strategies will be assessed with the Measure of Stimulus Control. Satisfaction with the FitLink program will be assessed with the Treatment Acceptability Questionnaire.

Moderators

Relationship quality will be measured with items adapted from the client version of the Working Alliance Inventory-Bond Subscale. Ratings will be completed separately for the relationship with the coach, the LM group, and the designated friend/family support

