person, with adaptation in wording as needed, yielding scores for each party. Most mediators and the moderator are only measurable once treatment has begun (e.g., coaching quality, social comparison with the LM group, and quality of the relationship with the group cannot be rated at pretreatment). Therefore, the “baseline” administration of such variables will occur at month 3 of treatment, with analyses controlling for weight loss achieved from months 0-3 as appropriate.

Qualitative data

Semi-structured interviews ($n = 30$) will be conducted at post-treatment to gather qualitative information about index participant experiences. 30 of the 320 index participants will be randomly selected with representation across conditions, age, sex, and race/ethnicity; additional interviews will be conducted if saturation is not reached. Interviews will last 45-60 minutes and will be digitally recorded and transcribed verbatim.

Optional Ecological Momentary Assessment- Wave 1 Only

Wave 1 participants *only* will have the opportunity to take part in a five-day ecological momentary assessment (EMA) to learn more about participants’ thoughts and feelings about self-monitoring their weight, their weight loss trajectory in the program so far, and whether these responses differ by treatment condition (i.e., based on which sources of support they have been sharing their self-monitoring data with). Participants will be paid an additional \$75 for completing this optional assessment and will lose \$3 for every survey they do not complete.

Wave 1 participants will be verbally informed about the opportunity to complete the optional additional assessment by their coaches. All Wave 1 participants will be emailed a revised informed consent through RedCap that includes the information on this additional assessment. All participants will digitally read and submit and revised informed consent. After, they will indicate whether or not they would like to opt-in to the study. Those who do not want to participate will exit the RedCap survey. Those who do want to participate will be asked to complete a 5-minute survey that asks about their overall satisfaction with weight loss so far, their lowest weight during the program, and their current weight loss goals (maintain, lose a little more, lose a lot).

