Coaches will have a minimum of masters-level training in psychology or a related field and will have experience conducting LM. We anticipate that many of the coaches will be existing members of the research staff who provide intervention for other research studies within the WELL Center. If needed, we will hire additional coaches for this study by advertising the position. Coaches are not participants. Coaches will be balanced across conditions. Initial training, as well as quarterly retraining to prevent drift, will include role plays of session content. Weekly supervision will be conducted. Using a structured rubric, 15% of each coach’s group sessions, phone calls, and text messages will be rated for fidelity to the treatment protocol. The rubric will take into account treatment integrity (delivering treatment as intended) and differentiation (the intended separation of study arms). Any coach deviations from the protocol (i.e., fidelity rated at <90%) will be tagged during review and addressed in supervision and retraining sessions.

Intervention and Assessment: Friends/Family Members

Friends/family members are asked to attend a webinar (held in Month 1 of the program, over Zoom), where they will learn how to provide support for the index participant’s lifestyle modification. Following the workshop, they will receive monthly text messages for a period of 2 years (24 message exchanges in total) that will prompt them to provide support to the index participant. Depending on which condition the index participant is assigned to, the messages may include information about the index participant’s food intake, exercise, and weight data. Friends/family member also will be asked to participate in three booster zoom meetings (one at month 6, one at month 12, and one at month 18) to receive additional guidance and tips about how to provide support.

Friends/family members are not asked to complete any assessment tasks or measures.

a) Data and Specimen Banking

Does not apply.

b) Data Management

Data Collection, Storage, and Quality Control

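### Coaching quality is a poor participant-level change mediator for Coach Share: its month-3 baseline and its month-12 value rest on different kinds of contact

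*Protocol*

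**What the plan says.** Four statements in the protocol bear on this point.

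- **Measure** (section 11 g, Mediators): "Coaching quality will be assessed by rating 15"% of the group sessions, texts and calls of each coach. The 15% is set per coach. No quota per participant or per period is given.
- **Role** (Statistical Analysis, Aim 2): "coaching quality will be examined as a mediator for Coach Share ON vs. OFF".
- **Metric** (Aim 2): "Analyses will determine if change in potential mediators from baseline to 12 months predict weight loss at 24 months".
- **Baseline** (section 11 g, Moderators): the protocol notes that "coaching quality, social comparison with the LM group, and quality of the relationship with the group cannot be rated at pretreatment", and that the baseline "administration of such variables will occur at month 3 of treatment".

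The contact schedule is in the opening summary, section 7 (Background) and section 11 g (Uniform Components). Groups meet weekly in months 1-3. Quarterly groups, two calls per quarter and monthly coach texts are listed for months 4-24. Training and Supervision adds that coaches are balanced across conditions.

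**The concern.** Coach Share is assigned to individual participants, so a mediator of it is most useful if it varies between participants and is measured in the same way at both ends of the change score. Neither is secured here. At month 3 the only rated contact type that has taken place is the group session, and its rating is the same for everyone in the group. By month 12 the rated material also includes one-to-one calls and texts. The difference between the two values mixes any change in coaching with a change in what is being rated. Aim 2 expects participants with sharing on to hold a high level of the mediator while those with sharing off decline, and this score is a weak test of that pattern.

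Because the sample is drawn per coach, some participants may also have little or no rated individual contact. At stake is the one Aim 2 test of whether Coach Share acts through the quality of coaching.

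**Working it through.** **Inputs from the protocol.** 320 index participants; 15% of each coach's contacts rated; weekly groups in months 1-3; then one group and two calls per quarter and one coach text per month.

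**Assumptions.** Each contact is drawn independently with probability 0.15; a monthly coach text counts as one contact; the 15% applies evenly over contact types and time. The protocol fixes only the 15% per coach.

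**Reproducing the stated schedule.**
- Calls: 2 x (21 / 3) = 14, as stated.
- Group sessions: 13 weekly (taking months 1-3 as 13 weeks) + 7 quarterly = 20, as stated.

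**Month-3 baseline.**
- Calls and coach texts in months 1-3: 0, so no participant has a rated individual contact.
- Group sessions rated: 0.15 x 13 = 1.95 expected per group, shared by all members.

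**Months 4-12, per participant.**
- Individual contacts: 6 calls + 9 texts = 15; expected rated 0.15 x 15 = 2.25.
- No rated call or text: 0.85^15 = 0.087, about 28 of 320.
- No rated call: 0.85^6 = 0.377, about 121 of 320.
- Nothing rated when the 3 quarterly groups are counted too: 0.85^18 = 0.054, about 17 of 320.

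**If the month-12 value means months 10-12 only** (2 calls + 3 texts).
- No rated individual contact: 0.85^5 = 0.444, about 142 of 320.

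**Moving the baseline to months 4-6 does not rescue the change score.**
- A rated individual contact in both months 4-6 and months 10-12: (1 - 0.444)^2 = 0.309, about 99 of 320.

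**Using a coach-level score.** If balanced coaches means that each coach serves sharing-on and sharing-off participants in similar proportion, the two sides receive about the same coach scores. The path from condition to mediator is then near zero by construction.

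**What the same rating effort could provide in months 4-12.**
- Calls: 0.15 x 6 x 320 = 288. Texts: 0.15 x 9 x 320 = 432. Total 720, or 720 / 320 = 2.25 per participant.
- Two each needs 640, so the total suffices. With 288 calls spread one per person, 320 - 288 = 32 participants (10%) have texts only.
- Texts then needed: 288 x 1 + 32 x 2 = 352, within the 432 available.

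**The case against.** **Aggregation belongs in the analysis plan.** The protocol does not say that the draw is unstratified or how ratings become a score, and a statistical analysis plan could settle both. That stands for the aggregation rule. But the protocol itself fixes the month-3 baseline and the change metric, and no analysis plan can supply month-3 ratings of calls that had not begun.

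**Unrated does not mean lost.** Group ratings are ratings too, which lowers the share with nothing rated in months 4-12 to about 5%. If the draw is random, unsampled participants are missing by design, and the protocol plans likelihood methods and multiple imputation. This stands. A reader might infer that the mediation test would be undefined or impossible to interpret; the documents do not support that. A group rating can be assigned to each member as a baseline, though it is then not comparable with the month-12 value.

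**Some individual contact may come before month 4.** The Coach Share description mentions individual weigh-ins without timing, and Uniform Components refers to regular coach texts without a start month. So one should not infer that no individual contact exists by month 3. Weigh-ins, however, are not a rated contact type. Even if monthly coach texts began in month 1, 0.85^3 = 61% of participants would have none of the three rated.

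**Overlap with the fidelity check.** Training and Supervision describes a fidelity rubric for the same 15% and the same contact types, which includes an element on separation of the arms. A reader might infer that the mediator score therefore contains the arm label. The protocol does not say so: coaching quality has a rubric adapted from a named checklist, and nothing identifies it with the fidelity rubric.

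**Conclusion.** The point holds in a limited form. As specified, the coaching-quality change score compares a group-level baseline with a later value that adds individual contacts, so it is not like-for-like. In months 4-12 about 9% of participants would have no rated individual contact and about 38% no rated call, or about 5% nothing rated once groups are counted. These shares rest on independent draws, one coach text per month and an even 15% across contact types. Thin ratings cost precision, and the noise in them attenuates the indirect effect.

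It would go too far to conclude that coaching quality cannot serve as a mediator at all. A score limited to months 4-12 would exist for about 91% of participants even with no change to the sampling. The weakness lies in the metric and the draw. It concerns one of several Aim 2 mediators and leaves the primary weight analysis untouched, so this is a desirable improvement and not an essential correction.

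**What to change.** 1. Draw the same 15% of calls and texts stratified by participant, so that each has at least two rated individual contacts in months 4-12.
2. Define the mediator as the mean level of coaching quality over months 4-12, adjusted for weight loss from month 0 to month 3, in place of change from month 3.
3. Let the score account for contact type (for example by standardising within calls and within texts), since about 10% of participants would have texts only.

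The cost is a changed sampling rule, a sentence in Aim 2, and the small burden of tracking the draw by participant. The number of ratings stays the same. For contacts already past, the new draw is possible only where recordings or message logs were kept.
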